Family-centred care (FCC) is, in fact, developmentally supportive care that helps develop bonding (12). Intermittent kangaroo mother, as a part of FCC, benefits from maternal-neonatal bonding (13). Similarly, the role of maternal involvement in pre-feeding sensorimotor stimulation is a hidden corner in research. To our knowledge, not even a single international or national study is available in this regard.

In resource-constrained setups with limited properly trained speech therapists and neonatal nurses, mothers can be involved in pre-feeding sensory motor stimulation after training and teaching to improve their feeding performance. Within this context, the current study aims to determine the following: 1) the maternal role in sensory-motor stimulation for oral feed establishment in preterm neonates, 2) determine the effect of sensory-motor stimulation offered by the mother on the onset of oral feeding, and 3) the efficiency of mother-mediated stimulation techniques on oral feeding compared to trained nurses.

Keywords

Prematurity sensory-motor stimulation oral feed establishment, feeding intervention

Material and methods

An interventional, prospective, randomized control trial was conducted after ethical approval from the Institutional Review Board of Fatima Memorial Hospital (FMH-07-2021-IRB-929-M). The authors confirm that this intervention's ongoing and related trials are registered in the ClinicalTrials.gov platform—accession number NCT05484726. The study protocol can be accessed at <https://www.clinicaltrials.gov/ct2/show/NCT05484726>.

Study hypothesised that preterm babies who receive sensory motor stimulation from their mothers as compared to trained nurses, are

- Start taking oral feed at the same time as compared to the control group
- Take the same amount of milk at the commencement of oral feeding
- Take milk with equal efficiency
- Not face more adverse effects

The study period spans 16 months, from March 2022 to July 2023, in the department of Neonatology, Fatima Memorial Hospital, Lahore. We enrolled all preterm neonates of gestation age 28 to 34 weeks who were admitted to NICU during the study period after seeking consent from parents or guardians. All these neonates were haemodynamically stable, established gavage feed, had no respiratory distress, no need for respiratory support except LFNC and did not receive any kind of analgesics at time of enrollment.

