However, all those neonates having major anomalies incompatible with life, major malformations, syndromic babies, cleft lip and palate, genetic disorders, haemodynamically unstable babies including IVH (grade III & IV), haemodynamically significant PDA (HsPDA) requiring antifailure therapy, NEC (stage II & III) or anemia requiring blood transfusion. All those neonates with adverse events including cough with choking, breath holding, choking, aspiration, tachycardia HR > 200/min, bradycardia HR < 100/min, apnea > 15 sec, tachypnea RR > 70/min while stimulation or feeding were excluded.

Protocol

Interventional Study Model: Factorial Assignment

- Maternal involvement in perioral sensory-motor stimulation be in three stages
 - Observer status
 - Performing under supervision
 - Independent
- Intervention period: 5 days as
 - Training phase (T): T1 and T2 (for mothers by the nurse)
 - Direct feeding phase (D): F1, 2, and 3 (oral feed was offered to neonate)
- Stimulation for 7 minutes and 15 minutes before feeding twice a day at 1100 and 1700 hrs.
- Two groups
 - Intervention group (G I): by mothers
 - Control group (G II): by staff nurses

Number of Arms: 2

Masking: Single (Care Provider)

The mothers, medical staff involved in general care, nursing staff involved in the intervention, and doctors conducting the assessment of oral feeding skills (OFS) were all blinded to allocation. The nursing staff was informed at the time of intervention that participating infants received either sensory motor stimulation or sham oral stimulation depending on group allocation.

Allocation

Randomization was done using a random Alloc Software environment. Gestation age-based stratification was done using 3 blocks design of 28 to 30, 30+1 to 32 & 32+1 to 34. Random allocation of neonates into the intervention or control groups by stratum using lottery method.

Blinding

The mothers, medical staff involved in general care, nursing staff involved in intervention and doctors conducting the assessment of oral feeding skills (OFS) were all blinded to allocation. The nursing staff was informed at the time of intervention that participating infants received either sensory motor stimulation or sham oral stimulation depending on group allocation.

Sample size

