The sample size was 46 (23 each in interventional and control groups) and calculated with a 95% confidence level, 10% margin of error and 5% level of significance by taking feeding-related problems as 40%. It was done by using openepi.com.

Initially only 46 neonates were enrolled in study. But later an immense maternal response was observed. Mothers were ready to learn and involve in sensory motor stimulation of their neonates. Hence, the final total study population size was 97 with 49 in experimental and 48 in control group.

Procedure of intervention

- The study intermediation was started not before 30 weeks of postmenstrual age when full gavage feeding was established with the addition of supplements.
- All mothers in this study was involved in gavage feeding before involvement in the procedure.
- Trained nurses taught details of sensory-motor stimulation to mothers in easily understandable languages (annexure 1 in (a) English and (b) Urdu). This procedure has been adapted from modified from PIOMI and Fucile (14,15).
- Stimulation was done for 7 minutes and at least 15 minutes before feeding twice daily at 1100 and 1700 hrs till full oral feed establishment (expected time 28 days chronological age)
- Oral feeding was offered using a bottle with a slow-flow nipple.
- Time monitoring for feeding was strictly followed
- Infants was fed for a maximum of 20 min, and feeding was discontinued early if adverse events occur.

Arms and intervention

- Study groups for sensory motor stimulation (5 minutes) + pacifier (2 minutes)
 - Intervention group (G1) : by mothers
 - Control group (G 2) : by staff nurses

Experimental: Intervention group (Group 1)

- Maternal involvement was done in three stages for the intervention group as
 - Observer status
 - T1: Nurses performing all steps while mother observer status
 - T2: Nurses perform all steps in front of the mother and a pacifier was offered by the mother
 - Performing under supervision
 - D1: Mother performs all steps and oral milk was offered by the nurse while the mother observes.
 - D2: Mother performing all steps and offering oral milk while the nurse is supervising

- Independent
 - D3: Mother performing all steps independently
- Study groups for sensory motor stimulation
 - Assigned intervention perioral sensory motor stimulation Step 1 - 6 over 5 minutes + pacifier 2 minutes for total duration of 7 minutes.

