 - Volume taken during the first 5 min (TV₅) out of total feed taken orally
 - Rate of transfer (RT) ml/min i.e., how long it neonate takes to finish oral feed.
 - Overall transfer (OT percent) volume taken/total volume prescribed. It shows trend towards oral feed establishment.
 - Proficiency (PRO percent) volume taken during the first 5 min/total volume prescribed.
 - SSB (Suck Swallow Breaths) coordination coordinated, developed pattern of suck swallow and breathe. It is a subjective assessment.

Statistical analysis

The statistical software IBM SPSS Statistics version 21 (SPSS, Chicago, IL) was used for the statistical analysis of the data. Appropriate bivariate analysis was performed to identify the unadjusted differences between the cases and controls. Categorical variables were expressed as frequencies and percentages. According to Shapiro Wilk test all continuous variables were asymmetrically distributed. Mann–Whitney U test was used for nonparametric continuous variables and were described as medians and inter quartile range (IQR). Fisher exact/Chi square test was used to compare categorical variables. Mann-Whitney test was used to compare continuous variables. The p-value of < 0.05 was taken as statistically significant.

Results

During the research period, 1009 newborns were admitted to the Neonatal Intensive Care Unit (NICU). Among them, 142 were born prematurely, with gestational ages falling between 28 and 34 weeks. Out of the preterm neonates, a total of 130 were eligible for the study, as 12 had to be excluded for various reasons. These exclusions included 2 cases where mothers experienced serious postnatal complications, 1 instance of parental refusal to participate, 1 case with incomplete data, and 8 cases that did not meet the inclusion criteria due to different reasons such as syndromic features, cleft lip and palate, suspected inborn error of metabolism (IEM), intraventricular hemorrhage (grade IV), and hemodynamically significant patent ductus arteriosus (HsPDA). Consequently, 130 neonates were included in the study and randomly assigned, with 65 in each group for intervention and control. Sensory motor stimulation (SMS) was administered to 107 of these neonates, and the study was completed with 97 neonates (as illustrated in Figure 1).

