Seizures ^a	7 (58.3%)	5 (41.7%)	0.394		
M A T E R N A L	Age ^b	29 (26 - 32)	30 (26.5 – 33)	0.138	
	Gravidity ^a	Primigravida	20 (43.5%)	26 (56.5%)	0.350
		2-3	22 (59.5%)	15 (40.5%)	
		≥ 4	7 (50.0%)	7 (50.0%)	
	Education ^a	Uneducated	2 (50.0%)	2 (50.0%)	0.699
		Primary	11 (52.4%)	10 (47.6)	
		Secondary	15 (42.9%)	20 (57.1%)	
		Higher	21 (56.8%)	16 (43.2%)	
	Previous preterm (yes) ^a	42 (52.5%)	38 (47.5%)	0.281	
	Job status (Housewife) ^a	29 (48.3%)	31 (51.7%)	0.368	
Hypertensive disorder ^a	29 (47.5%)	32 (52.5%)	0.290		
DM ^a	17 (50.0%)	17 (50.0%)	0.555		
Anemia ^a	25 (54.3%)	21 (45.7%)	0.304		

Table 2 : Feeding characteristics

Feeding characteristics	Experimental group (n=49)	Control group (n = 48)	p-value
PMA at enrollment (week)	32 (31 – 33)	32 (31 – 33)	0.787
ChA at enrollment (days)	13 (6 – 14)	9 (7 – 16)	0.925
Time to full gavage feed (days)	7 (5.5 – 13.5)	7 (6 – 14)	0.726
Discharge weight (kg)	1.48 (1.42 – 1.66)	1.48 (1.43 – 1.75)	0.698
Weight at enrollment (kg)	1.35 (1.25 – 1.54)	1.35 (1.21 – 1.60)	0.610
Duration of stay in NICU (days)	21 (15 – 29.5)	30 (16 – 30.75)	0.848
Milk Feed (ml/kg/day)			
Milk feed D1	120 (120 – 120)	120 (120 – 120)	0.302
Milk feed D2	120 (120 – 140)	120 (120 – 140)	0.871
Milk feed D3	140 (140 – 140)	140 (140 – 157.50)	0.109
Milk feed D5	150 (150 – 160)	160 (150 – 160)	0.361
Milk feed D7	160 (160 – 160)	160 (160 – 160)	0.184
Milk feed D14	160 (160 – 180)	160 (160 – 180)	0.758
Volume of feed prescribed (ml/feed)			
Volume prescribed D1	14 (12 – 15.5)	14 (12 – 16)	0.670
Volume prescribed D2	14 (12 – 17.5)	12.5 (12.25 – 19)	0.825
Volume prescribed D3	16 (14 – 17.5)	14 (14 – 20)	0.569
Volume prescribed D5	17 (15 – 19)	17 (15 – 21)	0.758
Volume prescribed D7	18 (16 – 20.5)	18 (16 – 22)	0.614
Volume prescribed D14	18 (16 – 22)	18 (16 – 24)	0.933

Table 3 : Study outcome

Outcome		Experimental gp (n=49)	Control gp (n=48)	p-value
Time to full oral feed (days)		10 (7 – 13)	9 (7 – 13)	0.531
Adverse events	D1	36 (53.7%)	31 (46.3%)	0.234
	D2	14 (50.0%)	14 (50.0%)	0.563
	D3	12 (50.0%)	12 (50.0%)	0.570
	D5	2 (100%)	0 (00%)	0.253
	D7 & 14	0 (00%)	0 (00%)	NA
L4 Efficacy on	D 1 -3	0 (00%)	0 (00%)	NA
	D5	12 (57.1%)	9 (42.9%)	0.331
	D7	16 (51.6%)	15 (48.4%)	0.528
	D14	35 (49.3%)	36 (50.7%)	0.434
Volume Taken Each feed	D1	2.0 (2.0 -7.0)	2.0 (2.0 -7.0)	0.803
	D2	5.0 (2.0 - 9.0)	3.0 (2.0 – 7.0)	0.558
	D3	7.0 (3.0 – 11)	4.0 (3.0 – 10.0)	0.540
	D5	8.0 (5.0 – 15)	6.5 (5.0 – 15)	0.521
	D7	9.0 (7.0 – 18)	7.5 (7.0 – 20)	0.951

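### Allocation was stratified by three gestational-age bands, but no outcome comparison uses them: a loss of precision of unknown, possibly small, size, with no inflation of type I error

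*Combined protocol and SAP*

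**What the plan says.** The Allocation section of the combined protocol and SAP sets three gestational-age bands: "Gestation age-based stratification was done using 3 blocks design of 28 to 30, 30+1 to 32 & 32+1 to 34". It adds: "Random allocation of neonates into the intervention or control groups by stratum using lottery method". It names both allocation software and a lottery, and gives no block size.

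The Statistical analysis section states: "Appropriate bivariate analysis was performed to identify the unadjusted differences between the cases and controls". Continuous variables are compared by Mann-Whitney. For the rest, "Fisher exact/Chi square test was used to compare categorical variables". No stratified test, regression or by-band table appears. The section gives 0.05 as the threshold and does not say whether tests are one- or two-sided.

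In the results, gestational age appears only as a baseline row of Table 1: median 30 (29 to 32) weeks in the experimental arm and 31 (29.3 to 32) in the control arm. Table 3 gives crude medians or counts with a p-value, and no confidence intervals.

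**The concern.** A factor is normally stratified on because it is thought to predict the outcome, and an analysis that ignores it gives up whatever precision it could have bought. That matters more here than in a trial seeking a difference. The hypotheses are of sameness, for example "Take milk with equal efficiency", and the Results call feeding skills in the two arms comparable. Such a reading is only as good as the precision behind it, and Table 3 shows none.

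Where arms are balanced within prognostic bands, an unadjusted test is also conservative, which makes a non-significant result more likely. In this trial a non-significant result is the hoped-for one.

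**Working it through.** **1. Reproducing reported figures.** The primary p-value (0.531, Mann-Whitney) cannot be rebuilt from medians and quartiles. The categorical values can be checked from the counts in Table 3, with 49 and 48 infants:

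| Row | Counts | Reported p | Fisher one-sided | Fisher two-sided |
|---|---|---|---|---|
| L4, D14 | 35 v 36 | 0.434 | 0.434 | 0.819 |
| Adverse events, D1 | 36 v 31 | 0.234 | 0.234 | 0.385 |
| Adverse events, D5 | 2 v 0 | 0.253 | 0.253 | 0.495 |
| L4, D5 | 12 v 9 | 0.331 | 0.331 | 0.623 |
| SSB, D2 | 33 v 27 | 0.180 | 0.180 | 0.300 |

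Of the 12 categorical rows in Table 3 with a p-value, 11 match the one-sided value in the direction of the observed difference. The exception is SSB at D3: reported 0.746, one-sided 0.557, two-sided 1.0.

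**2. Precision of the unadjusted comparisons.** Newcombe 95% intervals combine the Wilson limits (l, u) of each proportion: lower limit = d − √[(p1 − l1)² + (u2 − p2)²], upper limit = d + √[(u1 − p1)² + (p2 − l2)²].
- L4 at D14: 71.4% v 75.0%. Wilson limits are 57.6 to 82.1% and 61.2 to 85.1%. The difference is −3.6 points (−20.7 to 13.9).
- D1 adverse events: 73.5% v 64.6%. The difference is +8.9 points (−9.3 to 26.4).

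**3. Type I error.** This was simulated with 10,000 runs per cell, 97 infants analysed, and assumed band shares of 48/32/20%. Bands explain a share R² of outcome variance of 0, 3, 6, 12 or 27%. With a normal outcome, arms balanced within bands at randomisation and 33 of 130 then lost at random, the Mann-Whitney size is 5.3, 4.8, 4.5, 4.0 and 2.8%. If balance within bands is not forced, it is 5.1% throughout. Allowing for simulation error, neither case shows inflation.

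**4. What the bands could buy on transition time.** SD = IQR/1.349 = 6/1.349 = 4.45 days. This is a normal rule and so an assumption, since "According to Shapiro Wilk test all continuous variables were asymmetrically distributed". SE = 4.45 × √(1/49 + 1/48) = 0.903, and the half-width is 1.96 × 0.903 = 1.77 days. Multiplying by √(1 − R²) gives 1.72, 1.66 and 1.51 days at R² = 6, 12 and 27%.

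Simulated power for an assumed 2-day shift, unadjusted v van Elteren; ranges cover balanced and unforced allocation:

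| R² | Normal outcome | Skewed (gamma) outcome |
|---|---|---|
| 0% | 55–56% v 54–55% | 63% v 61–62% |
| 3% | 57% v 56–57% | 62–63% v 62–64% |
| 6% | 57% v 58% | 63% v 65% |
| 12% | 57% v 61–62% | 62% v 67–68% |
| 27% | 57% v 69–70% | 60–61% v 76% |

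Break-even is near 3%. For a binary outcome such as L4 at D14 (assumed 75% v 55%), chi-square v Cochran-Mantel-Haenszel power is 55% v 53–54% with no band effect, and 56–57% v 63–64% with the strongest band effect tried (assumed control-arm rates of 58, 86 and 97% across bands).

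**5. The estimate may move.** For p = 0.531, z = 0.6265, which on this scale is a difference of 0.6265 × 0.903 = 0.57 days. Under the assumed shares, band number (0, 1, 2) has mean 0.72 and variance 1.12 − 0.72² = 0.60. The step in outcome between bands is therefore √(R² × 4.45²/0.60) = 1.41, 1.99 and 2.98 days at R² = 6, 12 and 27%. Suppose one arm lies on average 0.1 band lower, and lower gestation means slower transition.

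| R² | Adjusted SE (days) | p, estimate unchanged | p, experimental arm lower (difference) | p, control arm lower (difference) |
|---|---|---|---|---|
| 6% | 0.876 | 0.52 | 0.63 (0.43) | 0.42 (0.71) |
| 12% | 0.847 | 0.50 | 0.66 (0.37) | 0.37 (0.76) |
| 27% | 0.772 | 0.46 | 0.73 (0.27) | 0.26 (0.86) |

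The direction depends on balance within bands, which is not reported.

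**The case against.** The strongest reply is that this may be worth almost nothing. No part of the document shows that the bands predict transition time. "The study intermediation was started not before 30 weeks of postmenstrual age when full gavage feeding was established", and Table 2 gives post-menstrual age at enrolment as 32 (31 to 33) weeks in both arms, so some of the maturity difference between bands was already removed at entry. At R² of 6 to 12% the half-width shrinks by 0.05 to 0.11 days on an outcome counted in days. Below about 3% the stratified test is slightly worse. The power figures rest on a 2-day shift, band shares and variance shares that the document does not give, and the half-widths are for a difference in means, not a Hodges-Lehmann difference. All of this stands, and it is why the point is minor. It does not remove the case for a cheap by-band table, which is what would show whether the bands matter.

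It is also fair that intervals could be added without stratifying, and that the missing margin is the larger fault.

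A reader might infer that ignoring the strata makes the reported tests invalid. The simulation does not support that. A reader might also infer that adjustment would leave the primary result as it is, because with the estimate held fixed the bands would need to explain 1 − (0.6265/1.96)² = 90% of variance to bring p to 0.05. That condition cannot be assumed: the medians (30 v 31 weeks, 10 v 9 days) allow the estimate to move, and nothing establishes balance within bands among the 97 of 130 analysed.

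**Conclusion.** The mismatch is certain: allocation used three bands, and no outcome comparison does. Its cost is precision and not type I error. Its size is unknown and possibly small: on the assumptions above, nothing at R² near 3%, and 0.26 days off a 1.77-day half-width at 27%. Adjustment could raise or lower the primary p-value, and the document does not allow either to be predicted.

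The one-sided p-values are a separate reporting fault that must be settled before a stratified column can sit beside Table 3. They rest on the reported counts alone. Two-sided values are larger in every row that matches a one-sided test, so no finding of non-significance is overturned. Severity is minor.

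**What to change.** 1. Keep the unadjusted comparisons, but restate the categorical p-values as two-sided and say so in the Statistical analysis section. Include Table 1, where for example sex at 0.239 is also a one-sided value (two-sided 0.419). Recheck SSB at D3.
2. Beside them add a band-stratified analysis, labelled post hoc because results are already known. Take the bands from the randomisation records: gestational age was collected in weeks, while the bands change at 30+1 and 32+1.
3. For transition time and the continuous feeding-skill outcomes (TV, TV5, RT, OT, PRO), use the van Elteren test with a stratified Hodges-Lehmann difference and 95% CI.
4. For L4, adverse events and SSB coordination, use Cochran-Mantel-Haenszel with a stratified risk difference and 95% CI. Use the exact version where counts are sparse, as for D5 adverse events (2 v 0). Omit rows where every infant has the same value: L4 on D1 to D3, adverse events on D7 and D14, and SSB on D14.
5. Report the number of infants and median transition time per band and arm.

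The cost is one re-run on data already held, plus about 1 to 2 power points in the added column if the bands turn out not to be prognostic. As a post hoc supplement it cannot replace the unadjusted tests, and it does not supply the equivalence margin that the hypotheses of sameness need.

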- Hemodynamically significant patent ductus arteriosus (HsPDA) diagnosed by echocardiography
- Necrotizing enterocolitis (NEC) diagnosed using modified Bell's scoring (stage 1)
- Feeding intolerance diagnosed as aspirates > 20% of previous feed ± abdominal distension of > 2cm from base line
- Sepsis (leukocytosis or leukopenia or ANC<150 along with raised CRP and platelets <100 and or positive blood culture)
- Seizures
- Discharge weight in kg
- Duration of stay in NICU in days
- Neonatal feeding characteristics at time of enrollment in study include
 - Postmenstrual age (PMA) measured in weeks
 - Chronological age (ChA) measured in weeks
 - Time/duration to achieve full gavage/tube feed measured in days
 - Daily milk intake (ml/kg/day) when sensory motor stimulation was started
 - Volume of feed prescribed for each feed (ml)

The **outcome** measured were documented daily twice a day (11.00 and 17.00 hrs) until achievement of full oral feed. Full oral feed was volume of 120-140ml/kg/day taken orally. However, to make calculations concise, for both groups, all outcome parameters were documented on proforma for fixed time (11.00 am) for D1, D2, D3, D5, D7 and D14.

- Primary Outcome Measure
 - Transition time to full oral feeding is the time interval between commencement of perioral sensory stimulation on D1 to establishment of full oral feed in both groups. It was done daily till 14th day of perioral sensory motor stimulation. Transition time to full oral feeding was the day at which baby was able to take oral feed of volume of 120-140ml/kg/day.
 - Improvement (change) in efficiency oral feed establishment in terms of amount and time. It was classified into four levels depending upon the level of maturity in ascending order as follows:
 - Level 1: PRO < 30% and RT < 1.5 ml/min
 - Level 2: PRO < 30% and RT ≥ 1.5 ml/min
 - Level 3: PRO ≥ 30% and RT < 1.5 ml/min
 - Level 4: PRO ≥ 30% and RT ≥ 1.5 ml/min

For our RCT, efficacy was measured as the achievement of L4 for the intervention group vs the control group.

- Adverse outcome monitoring was done for every neonate from first day of enrollment in study (D1) till establishment of full oral feed (by D14 expected). These include non-life threatening adverse events including cough, tachycardia HR 180-200/min, bradycardia HR120 - 100/min, , tachypnea RR 60 - 70/min while maintaining SpO2 of >90% at room air
- Secondary Outcome Measure:
 - Total volume (TV) taken during each feed

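### The sample size of 46 cannot be reproduced from its stated inputs, and those inputs describe the precision of one prevalence rather than sizing the mother-versus-nurse comparison

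*Combined protocol and SAP*

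**What the plan says.** The Sample size section of the combined protocol and SAP states: "The sample size was 46 (23 each in interventional and control groups"). It was "calculated with a 95% confidence level, 10% margin of error and 5% level of significance by taking feeding-related problems as 40"%, using OpenEpi. The section names no OpenEpi module, population size, design effect, power, second rate, or equivalence or non-inferiority margin.

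Enrolment then went beyond 46, for this reason: "But later an immense maternal response was observed". The final figure is 97, with 49 in the mothers' arm and 48 in the nurses' arm.

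The hypotheses in Material and methods are statements of sameness, among them "Take milk with equal efficiency" and "Not face more adverse effects". The primary outcomes are transition time to full oral feeding and feeding efficiency, where "efficacy was measured as the achievement of L4 for the intervention group vs the control group"; adverse events are listed with them, and the Results treat them as primary.

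The Statistical analysis section provides for group summaries and tests at p < 0.05, with no interval for a difference. The Results report no significant differences on the primary outcomes. They then call the mothers' group comparable on feeding skills: volume, rate, overall transfer, proficiency and suck-swallow-breathe (SSB) coordination.

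**The concern.** There are two problems, and the second matters more.

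First, a reader who puts the four stated inputs into the usual formula gets about twice the stated number.

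Second, the inputs answer a different question from the one the trial asks. A confidence level, a margin of error and one rate fix how precisely a single prevalence is estimated. The 5% significance level adds nothing to the 95% confidence level. The 40% appears to be the introduction's overall figure for preterm infants who have difficulty moving to oral feeding. It is neither an arm-specific rate nor a primary outcome.

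A trial that hypothesises sameness needs a margin, or at least an interval, to show which differences it can rule out. A non-significant p-value does not do that. At stake is whether the no-difference and comparability statements can be read as evidence that mother-delivered stimulation is no worse.

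**Working it through.** **1. The stated figure.** Inputs from the Sample size section: z = 1.96 (95% confidence), p = 0.40, d = 0.10.

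n = z² p(1 − p) / d² = 3.8416 × 0.24 / 0.01 = 92.2, so 93. The section says 46, so the figure is not reproduced.

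**2. Finite-population correction.** OpenEpi may have been given a population size N, so I tried

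n = N p(1 − p) / [(d²/z²)(N − 1) + p(1 − p)].

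- N = 87 gives 45.01, N = 90 gives 45.79, N = 91 gives 46.05 and N = 92 gives 46.30. The result is 46 for N = 87 to 90 if rounded up, or 89 to 92 if rounded to the nearest whole number.
- No such N is stated. The Results report that "1009 newborns were admitted to the Neonatal Intensive Care Unit (NICU). Among them, 142 were born prematurely" at 28 to 34 weeks, and that 130 were "randomly assigned, with 65 in each group for intervention and control". They also give 107 stimulated and 97 completed.
- Rounded up, those counts give: 97 → 48; 107 → 50; 130 → 55; 142 → 57; 1009 → 85. None gives 46.

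**3. Other undocumented routes.** A margin of d = 0.20 gives 3.8416 × 0.24 / 0.04 = 23.05, close to 23 per arm. Half of 92.2 is 46.1. Neither is stated.

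**4. Precision for one prevalence of 40%.** Half-width = 1.96 × √(0.24/n). For n = 46 it is 14.2 points without a population correction; for n = 97 it is 9.7 points.

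**5. What Table 3 leaves open between arms.** The printed percentages are shares of the row total (for example 12/21 = 57.1%), so I recomputed arm rates on 49 and 48. One-sided Fisher tests on these denominators, taken in the observed direction, return the printed p-values: 0.331, 0.528 and 0.434 for level 4 (L4); 0.234, 0.563 and 0.570 for adverse events on D1 to D3. This confirms the denominators.

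Wald 95% interval: (p₁ − p₂) ± 1.96 √[p₁(1 − p₁)/49 + p₂(1 − p₂)/48].

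| Outcome | Mothers | Nurses | Difference (points) | 95% interval |
|---|---|---|---|---|
| L4, D5 | 12/49 (24.5%) | 9/48 (18.8%) | +5.7 | −10.6 to 22.1 |
| L4, D7 | 16/49 (32.7%) | 15/48 (31.3%) | +1.4 | −17.2 to 20.0 |
| L4, D14 | 35/49 (71.4%) | 36/48 (75.0%) | −3.6 | −21.2 to 14.0 |
| Adverse events, D1 | 36/49 (73.5%) | 31/48 (64.6%) | +8.9 | −9.4 to 27.2 |
| Adverse events, D2 | 14/49 (28.6%) | 14/48 (29.2%) | −0.6 | −18.6 to 17.4 |
| Adverse events, D3 | 12/49 (24.5%) | 12/48 (25.0%) | −0.5 | −17.7 to 16.7 |

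Adverse events on D5 were 2 versus 0, too few for a Wald interval. Newcombe intervals agree closely where checked: L4 on D14, −20.7 to 13.9; D1 adverse events, −9.3 to 26.4.

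**6. Transition time.** Table 3 gives medians (IQR) of 10 (7–13) and 9 (7–13) days. A valid interval for the difference cannot be recovered from these. Turning an IQR into an SD assumes normality, and the Statistical analysis section says that all continuous variables were asymmetric.

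**7. Coverage.** Not analysed: 65 − 49 = 16 and 65 − 48 = 17, so 33 of 130 (25%).

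**The case against.** The strongest reply is that the trial is finished and its 97 infants give ±9.7 points at a 40% rate, inside the stated 10-point margin. That stands. The one-prevalence target was met in the end, and the gap between 46 and 93 changes no result. But the target was never about the comparison, and the intervals above already use all 97 infants.

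A second reply is that 46 may be a correct output with an unreported input. That also stands. A reader might infer that 46 is simply an arithmetic mistake, or that a population of about 87 to 92 must have been entered. The document supports neither inference: several undocumented routes lead to 46 or to 23 per arm. The supportable statement is that 46 is not reproducible from what is stated.

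Third, the word comparable in the Results is attached to the skill measures, not to transition time or adverse events. This is right, and L4 is linked to those measures only through proficiency and rate of transfer. The primary outcomes have their own no-difference sentence, however, and both statements rest on p-values alone.

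Fourth, Table 3 prints counts, so a reader can work out the intervals for the binary outcomes. True; the complaint is that they are not reported. For the continuous measures a reader cannot do so.

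A reader might also infer that mothers did worse. The intervals do not show that. All of those in the table include zero and extend in both directions.

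**Conclusion.** The point holds. The stated inputs give 93, not 46, and the document does not allow the reason to be identified. More lastingly, the calculation did not size the mother-versus-nurse comparison, the reason given for going beyond 46 is not a statistical one, and the sameness hypotheses have no margin or interval behind them. In the analysed infants, the 95% intervals do not exclude L4 rates lower with mothers by about 11 points (D5), 17 points (D7) or 21 points (D14), or D1 adverse events more frequent by about 27 points (26 by Newcombe).

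These figures assume that the 10% margin is an absolute half-width, that z = 1.96, and that Table 3's denominators are 49 and 48, which the p-value check supports. They describe the 97 completers and carry no uncertainty from the 33 randomised infants not analysed. This should be fixed; it calls for better reporting and a qualified conclusion, and it does not show that mother-delivered stimulation is inferior.

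**What to change.** - **Sample size section.** State the missing input or correct the error behind 46. If no further input was used, say that the listed inputs give 93 and that 46 does not deliver a 10-point margin. In either case, say that the calculation did not size the between-arm comparison and that the increase beyond 46 had no statistical basis.
- **Statistical analysis section and Table 3.** Report 95% intervals for the between-arm difference in L4 by day, adverse events by day, and transition time. For transition time, use a method that suits skewed data and handles infants not at full oral feed by day 14, when assessment ends. Add intervals for the measures that the Results call comparable: volume (total and first 5 minutes), rate of transfer, overall transfer, proficiency and SSB coordination.
- **Results.** State that the intervals cover 97 of the 130 randomised infants. Qualify the no-difference and comparability statements: no margin was set, and the differences given above are not excluded.

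The cost is some rewording and a short analysis of existing data. No new patients are needed. The downside is a less favourable stated precision for 46 and a more guarded conclusion.
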